STATISTICAL ANALYSES PLAN

Acute exercise and coronary heart disease risk markers in healthy male smokers and non-smokers

Version 1

Investigators

[name]

[name]

Address

School of Sport, Exercise and Health Sciences

Loughborough University

Leicestershire

[name]

United Kingdom

Correspondence

[name]: [name], [contact]

Statistical analyses plan

The data collected will be analysed using the software package SPSS (SPSS version 23, SPSS Inc., Chicago, IL). The distribution of the outcome variables will be explored using histograms. Normally distributed data will be presented as mean (SD). Variables deemed to show a positively skewed distribution will be natural log transformed prior to analysis, and negatively skewed variables will be reflected before natural log transformation. These data will be presented as geometric mean (95% confidence interval) and analysis will be based on ratios of geometric means and 95% confidence intervals for ratios.

Physical characteristics and exercise responses will be compared between smokers and non-smokers using linear mixed models with smoking status included as a fixed factor. The homeostasis model assessment of insulin resistance (HOMA-IR) will be calculated as follows (Matthews *et al.* (1985) *Diabetologia* 28: 412–419):

$$\text{HOMA-IR} = \frac{\text{Fasting glucose} \times \text{Fasting insulin}}{22.5}$$

Total area under the plasma concentration versus time curve (AUC) will be calculated for plasma constituents and blood pressure using the trapezoidal method. Linear mixed models will be employed to examine differences in dietary intake, habitual physical activity and sedentary time, HOMA-IR and fasting and AUC plasma constituents and blood pressure with condition (exercise versus control) and group (smokers versus non-smokers) included as fixed factors. Models for habitual physical activity and sedentary time will include wear time as a covariate. Differences in postprandial plasma constituents and blood pressure over time will be examined using linear mixed models repeated for condition, group and time.

Absolute standardised effect sizes will be calculated by dividing the difference between the mean values (exercise versus control or smokers versus non-smokers) with the pooled standard deviation. In the absence of a clinical anchor, an effect size of 0.2 will be considered the minimum important difference, 0.5 moderate and 0.8 large (Cohen 1988 *Statistical power analysis for the behavioural sciences*, 2nd edn., Lawrence Erlbaum Associates, Hillsdale (NJ)). Statistical significance will be accepted as $P < 0.05$.

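### The SAP picks raw or log scale from histograms of the outcomes, not from the residuals of the mixed models; the cost is modest, and a residual check is a cheap improvement (minor)

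*SAP*

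**What the plan says.** All the relevant text is in the SAP, under *Statistical analyses plan*.

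- The check: "The distribution of the outcome variables will be explored using histograms".
- Its consequence: "Variables deemed to show a positively skewed distribution will be natural log transformed prior to analysis". Negatively skewed variables are reflected first and then logged.
- The effect measure after logging: "analysis will be based on ratios of geometric means and 95% confidence intervals for ratios".
- The models for fasting and AUC values are linear mixed models "with condition (exercise versus control) and group (smokers versus non-smokers) included as fixed factors". Postprandial values over time "will be examined using linear mixed models repeated for condition, group and time".

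The SAP gives no numerical criterion for skewness and mentions neither residuals nor any check of a fitted model. It does not say whether the histograms pool groups, conditions or time points. It gives no sample size or standard deviation.

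**The concern.** A linear mixed model makes assumptions about its residuals and participant effects, not about the overall distribution of the outcome. A raw histogram combines spread between men, group and condition effects, and measurement error. It can look skewed when the residuals are normal. It can also look acceptable when the residual spread grows with the level.

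This matters because the check does more than set a numerical convenience: it decides whether a marker is reported as a difference or as a ratio. That decision rests on how a histogram of the trial's own outcome data looks to the analyst, one variable at a time. Nothing in the text prevents a marker from being a difference when fasting and a ratio for AUC, although nothing says this will happen.

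**Working it through.** The SAP states no figure on this point, so there is none to reproduce. The check has three steps. Every size below is an assumption, including that each man is measured under both conditions.

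**1. What the histogram weighs.** Within one group and condition, write an outcome as man's level + error, with between-man variance σ_b², error variance σ_e² and intraclass correlation ICC = σ_b²/(σ_b² + σ_e²). If level and error are independent, then

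skewness of outcome = ICC^1.5 × (skewness of levels) + (1 − ICC)^1.5 × (skewness of errors).

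With ICC = 0.8 the weights are 0.8^1.5 = 0.716 and 0.2^1.5 = 0.089, a ratio of 8 to 1. In the exercise-minus-control difference the man's level cancels and only error remains. So the histogram mainly describes a component that drops out of the exercise contrast, but which is central to the smoker contrast.

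**2. Additive within-man error, where the raw scale suits the exercise contrast.** Inputs: two groups of 8, 12 or 20 men; levels 1 + Gamma(1,1), with variance 1 and skewness 2; normal error with SD 0.25; a variable counted as skewed if the sample skewness of the pooled raw values exceeds 1; two-sided 5% tests; 4,000 simulated trials per setting. Here ICC = 1/(1 + 0.0625) = 0.941, so the skewness of the raw outcome is about 0.941^1.5 × 2 = 1.83 although the errors are normal.

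| Men per group | Rule chooses log (no effect) | Paired-difference residuals flagged (no effect) | Power, raw | Power, always log | Power, following the rule |
|---|---|---|---|---|---|
| 8 | 53% | 3.7% | 45.0% | 39.5% | 42.4% |
| 12 | 63% | 2.0% | 65.1% | 58.6% | 61.0% |
| 20 | 78% | 0.5% | 86.7% | 81.8% | 83.0% |

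Power is for an effect of 0.5 SD of the paired difference. The rule's losses against the raw scale are 45.0 − 42.4 = 2.6, 65.1 − 61.0 = 4.1 and 86.7 − 83.0 = 3.7 points. For 0.7 SD they are 73.6 − 70.9 = 2.7, 90.8 − 88.0 = 2.8 and 99.2 − 98.0 = 1.2 points. Over all effect sizes run, the rule chose log in 51% to 78% of trials. With no effect, rejection was 4.7% to 5.4% on the raw scale, 4.9% to 5.1% on the log scale and 4.8% to 5.2% under the rule. The simulation error is about √(0.05 × 0.95/4000) = 0.3 points, so type I error is unaffected.

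**3. Both error structures, and a residual check.** Inputs: 24 men, ICC 0.8, log-normal levels, an exercise effect of 0.3 SD, and skewness above 0.5 counted as skewed.

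- *Multiplicative error*, between-man log-SD 0.3 to 0.6: the rule chose log in 75% to 98% of data sets. Power was about 60% under the rule, against 57% falling to 47% on the raw scale. The rule therefore gains 60 − 57 = 3 to 60 − 47 = 13 points over never logging.
- *Additive error*: a check of residual spread against level chose log in 21% to 34% of data sets, against 41% to 69% for the histogram rule, which cost about 1 to 4 power points.
- Under both structures the residual check had power equal to or slightly above that of the histogram rule.

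The residual check has to look at spread against level as well as shape. Under multiplicative error the paired differences can be nearly symmetric while their spread rises with the level, and a histogram of residuals would miss this.

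**The case against.** The strongest objection is that the rule is common, declared in advance, leaves type I error intact, and often gives the right answer for concentrations, whose errors may well be proportional to the level. All of this stands. A simulation with only additive error is one-sided, because logging must lose there. Its size also depends on the setting: one additive run with log-normal levels gave losses of 2 to 7 points (60% to 58% at log-SD 0.3, 60% to 53% at 0.4). At log-SD 0.4, however, 22% of the data sets contained zero or negative values, which concentrations cannot take. The skewness cut-offs of 0.5 and 1 are inventions, since the SAP gives none.

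It also stands that skewed levels breach the model's participant-effect assumption, and that a raw histogram is informative for the between-man comparison of smokers and non-smokers. Silence about residual plots does not exclude them, and a residual plot is still read by eye.

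What survives is narrower. The stated rule examines the wrong quantity for the exercise contrast, and it fixes the estimand before any model is fitted.

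Two stronger readings are tempting. A reader might infer that exercise effects will be tested on the wrong scale. The SAP does not support this, because the error structure is unknown and logging may be right. A reader might also infer false findings that exercise acts differently in smokers. With assumed group means of 2 and 4 and a change of −0.5 in both, the group-by-condition contrast was rejected in about 5% of trials on the raw scale and in 43% to 85% on the log scale. But the SAP names no interaction term. The log-scale result is also no false positive: the ratios are 1.5/2 = 0.75 and 3.5/4 = 0.875, which differ. The example shows only that the two scales ask different questions.

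**Conclusion.** The point holds as a minor one. The SAP decides between a mean difference and a ratio of geometric means from raw outcome histograms, whereas the models depend on residual shape and spread. If each man is measured under both conditions, the histogram is a poor guide for the exercise contrast.

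Under assumed additive error the rule often logs without need and loses a few power points. Under assumed multiplicative error it performs well. Type I error for the exercise main effect stays near 5% in the scenarios run. The case for change rests mainly on a clearer, more consistent estimand and a more reliable choice of scale at almost no cost, not on a demonstrated error in the results.

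**What to change.** Replace the histogram rule with three statements.

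1. The scale for each marker is judged from residual and residual-versus-fitted plots of the fitted mixed model, with group and condition not identified on the plots. State the basis: log is chosen where residual spread rises with the fitted value, or residuals are right-skewed, and logging removes this. The fitted values should include the man's own level. For two-condition data, a plot of within-man difference against within-man mean serves the same purpose.
2. One scale per marker is used for its fasting, AUC and time-course analyses. The SAP should name which of these models decides.
3. The other scale is reported as a sensitivity analysis, so that a reader can see whether a conclusion depends on this still partly visual judgement.

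The cost is a few sentences, residuals saved from models already planned, and a second run of each model. The sponsor gives up the freedom to choose the scale variable by variable. A single scale per marker may also fit one of its three analyses slightly less well than the others.

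### For negatively skewed outcomes, the planned geometric mean and ratio describe K − X, not the marker, so the ratio runs backwards and depends on an unstated constant

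*SAP*

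**What the plan says.** The first paragraph of the SAP sets the distributional rules. The trigger is visual: "The distribution of the outcome variables will be explored using histograms". Two transformations follow. The first is a direct log: "Variables deemed to show a positively skewed distribution will be natural log transformed prior to analysis". For the opposite direction of skew the plan puts another step in front of the log: "negatively skewed variables will be reflected before natural log transformation". The next sentence covers how the transformed variables are reported: "These data will be presented as geometric mean (95% confidence interval) and analysis will be based on ratios of geometric means", with 95% confidence intervals for the ratios.

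That sentence follows both transformations and does not separate them. The SAP gives no reflecting constant, no step that undoes the reflection and no rule on which way a ratio of reflected values should be read. The last paragraph adds a second summary for every comparison: "Absolute standardised effect sizes will be calculated by dividing the difference between the mean values" by the pooled standard deviation.

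**The concern.** Reflection replaces X by K − X, with K above the largest observation. For a positive-valued marker a constant cannot be avoided, because ln(−X) is undefined. After that step, high values of the analysed variable mean low values of the marker. A reporting rule written for ln(X) then gives a geometric mean and a ratio for a different quantity, on a scale the analyst sets by choosing K.

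If an outcome is judged negatively skewed and the text is followed as written, a fall after exercise would be published as a ratio above 1, with a narrow-looking interval that does not refer to the marker. The planned effect sizes are absolute, so they carry no sign that would contradict it.

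**Working it through.** The SAP states no sample size, marker distribution or other figure on this point, so there is nothing of its own to reproduce. The check is algebra first, then two illustrations on assumed data.

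**Algebra.** Let Y = ln(K − X), with the same K in both conditions.

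- exp(mean Y) = GM(K − X), the geometric mean of K − X. It is not GM(X).
- exp(mean Y_exercise − mean Y_control) = GM(K − X_exercise) / GM(K − X_control).
- If X falls under exercise, K − X rises and the ratio goes above 1. If X rises, the ratio goes below 1.
- As K grows, ln(K − X) − ln K tends to 0 for every value, so the ratio tends to 1. As K approaches the maximum, the log of the smallest reflected value tends to minus infinity, so one observation dominates. The ratio can therefore be moved over a wide range by K alone.

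**Fixed example.** Assumed: 20 values per condition, X = 10 − c·exp(0.5z) at normal quantiles z, with c = 2.0 for control and 1.5 for exercise (skewness −1.08). Arithmetic means are 7.75 (control) and 8.32 (exercise), ratio 1.07. The ratio of geometric means of X is 1.08. The marker is higher under exercise. Intervals are unpaired t intervals on the log scale, a simplification of the planned mixed model.

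| K | Ratio under the SAP rule (95% CI) |
|---|---|
| max + 0.01 | 0.557 (0.286 to 1.082) |
| 10 | 0.750 (0.546 to 1.031) |
| max + 1 | 0.797 (0.620 to 1.025) |
| max + 10 | 0.953 (0.903 to 1.007) |

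At K = 10 the arithmetic is simple: GM(K − X) is 2.0 for control and 1.5 for exercise, so the ratio is 1.5/2.0 = 0.75. A rise of about 7% in the marker appears as a 25% fall. Un-reflecting the two centres gives 10 − 2.0 = 8.0 and 10 − 1.5 = 8.5, ratio 8.5/8.0 = 1.06, in the right direction. But 8.0 and 8.5 are not geometric means of X, and their ratio is not the exponentiated model contrast, so the model's interval does not belong to it. The P value moves little here (0.075 to 0.083 over these K).

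**Paired simulation.** Assumed: X1 = 10 − exp(N(0.5, SD 0.6)), with samples redrawn if any value is at or below 0.5; X2 = 0.9·X1 + N(0, SD 0.5), so the true ratio is 0.90; K = max(X1, X2) + constant, common to both conditions; paired t interval on ln(K − X2) − ln(K − X1), exponentiated; 5,000 runs.

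| | max + 0.1 | max + 1 | max + 5 |
|---|---|---|---|
| n = 24, median ratio | 1.87 | 1.39 | 1.13 |
| n = 24, median 95% CI limits | 1.46 to 2.41 | 1.26 to 1.53 | 1.09 to 1.17 |
| n = 24, CI wholly above 1 | 99.8% | 100% | 100% |
| n = 12, median ratio | 2.05 | 1.41 | 1.13 |
| n = 40, median ratio | 1.79 | 1.38 | 1.13 |

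The ratio exceeded 1 in every run at every K. Repeat runs agreed to within about 0.02. The mean difference on the original scale at n = 24 is −0.81 (−1.02 to −0.59): right direction, no K.

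**Smaller effect.** With a 3% fall at n = 24 (standardised effect about 0.20, the SAP's own minimum important difference), the median ratios are 1.13, 1.09 and 1.04 for the same three K. The ratio exceeds 1 in 85%, 97% and 99% of runs. The interval excludes 1 in about 25%, 46% and 58%, so here K affects the inference as well as the estimate.

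**The case against.** The strongest reply is that the reversal is easily undone. Take the ratio the other way up, GM(K − X_control)/GM(K − X_exercise), and invert the limits. That is the same contrast with its sign changed, it keeps the model's exact interval, and the SAP does not forbid it. An analyst who has reflected a variable knows that it runs backwards.

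This stands for direction only. Inverting the n = 24 results gives 1/1.87 = 0.53, 1/1.39 = 0.72 and 1/1.13 = 0.88 for one true ratio of 0.90. At max + 1 the inverted limits are 1/1.53 = 0.65 and 1/1.26 = 0.79, which exclude 0.90. The quantity is still on the K − X scale and still set by K, and the SAP does not state the step.

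Four further points are fair:

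- **It may never arise.** The SAP names no negatively skewed variable and the document identifies no primary outcome, so no effect on a main conclusion can be shown. This limits the severity. But the SAP wrote the contingency itself, for any outcome variable, and a planned rule should work when it is used.
- **The 10% example is a large effect.** Its standardised size is about 0.70 on the pooled SD. That is why the smaller case is shown; the figure of 1.87 should not be taken as typical.
- **Unsigned effect sizes do not prove that a reversal would go unnoticed.** Agreed. They only fail to reveal it.
- **The reporting sentence might be meant for direct logs alone.** Then reflected variables have no reporting rule, and the same edit is needed.

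**Conclusion.** The concern holds. The reporting rule is wrong as written for one of the two transformations it covers: it yields a geometric mean and ratio of K − X, reversed in direction relative to the marker and dependent on a constant that the plan leaves open. Both faults follow from algebra and need no data.

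Their size rests on assumed data, an assumed ceiling-type marker and an illustrative range of K. In those examples a true ratio of 0.90 is reported as 1.13 to 1.87 (n = 24), and a true rise of about 7% as a ratio of 0.56 to 0.95. The fault affects results only if some outcome is judged negatively skewed. It should be fixed before analysis. Directly logged and untransformed variables are not affected.

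**What to change.** Restrict geometric means and their ratios to variables that were logged directly. For negatively skewed variables, state one of two rules:

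1. Report mean differences with 95% confidence intervals on the original scale, using a robust or participant-level bootstrap interval if the model residuals are clearly non-normal.
2. If reflection is kept, fix K in advance and use the same K for all conditions and groups, use the transform for testing only, and report un-reflected summaries with the direction of the difference stated in words.

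The first is simpler because it removes K altogether. The second also meets the reporting concern, provided that no ratio of reflected geometric means is presented as a ratio for the marker.

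The cost is one or two sentences of SAP text and possibly slightly wider intervals for the affected variables. Nothing else in the analysis changes.

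### None of the exercise-versus-control models has a period (visit-order) term, so any shift between a man's two visits is left in the error and costs precision

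*SAP*

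**What the plan says.** The third paragraph of the SAP's section Statistical analyses plan lists the terms of each model containing condition. One sentence covers dietary intake, habitual activity and sedentary time, and then "HOMA-IR and fasting and AUC plasma constituents and blood pressure with condition (exercise versus control) and group (smokers versus non-smokers) included as fixed factors". The next-but-one sentence covers the curves: "Differences in postprandial plasma constituents and blood pressure over time will be examined using linear mixed models repeated for condition, group and time". Time here is time within the postprandial curve, not visit.

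The only further term is in the sentence between them: "Models for habitual physical activity and sedentary time will include wear time as a covariate". Period, visit order and sequence are not mentioned anywhere in the document.

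Physical characteristics and exercise responses (second paragraph) are analysed by "linear mixed models with smoking status included as a fixed factor". Those models compare smokers with non-smokers only, so period is not at issue there.

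**The concern.** The SAP does not use the word crossover. It does treat condition as a factor separate from smoking group, and it describes models that "will be examined using linear mixed models repeated for condition, group and time". The natural reading is that each man attends twice, once for exercise and once for control. The phrase is loose evidence, because it also lists group, which cannot vary within a man. The point is therefore conditional on this reading.

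On that reading, exercise minus control within a man equals the exercise effect plus or minus any first-to-second-visit shift, with the sign set by the order he followed. A model without period counts that spread as random error. The exercise contrast then has a larger standard error than the data warrant, in a plan where "an effect size of 0.2 will be considered the minimum important difference". If the orders are unequal among the men analysed, part of the shift also enters the estimate as bias.

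**Working it through.** **Inputs.** From the SAP: the model terms above, the 0.05 significance level (taken as two-sided, since sidedness is not stated) and the 0.2 SD threshold. The SAP gives no sample size, SD, correlation or power figure, so there is no stated figure to reproduce. Assumed: two visits per man, the man as the unit of repetition, 24 men in orders 12:12, outcome SD 1, correlation between visits rho = 0.7, exercise effect 0.4 SD. The visit shift is d within-person SDs, with d = 0, 0.25, 0.5 and 1.0.

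**Standard error.** The within-person variance is sw² = 1 − rho = 0.3. The variance of a man's exercise-control difference is 2sw² with period in the model and 2sw² + (d·sw)² without it, when orders are balanced. The ratio of standard errors is therefore √(1 + d²/2):

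- d = 0.25: √1.03125 = 1.016
- d = 0.5: √1.125 = 1.061
- d = 1.0: √1.5 = 1.225

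A finite-sample version that allows for the two smoking groups multiplies d² by N/(N − 2). At d = 1.0 this gives 1.265, 1.243 and 1.237 for 12, 24 and 36 men. The inflation thus hardly depends on sample size, and at 24 men the largest shift costs about 24%.

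**Power and type I error.** Without period, the standard error is √[(0.6 + 0.3d²)/24] and the noncentrality is 0.4 divided by it. Simulation used 200,000 trials per setting.

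| d | Noncentrality, no period | Noncentral-t power, no period | Simulated power, no period | Simulated type I error, no period |
|---|---|---|---|---|
| 0 | 0.4/0.158 = 2.53 | 0.678 | 0.680 | 0.050 |
| 0.25 | 0.4/0.161 = 2.49 | 0.665 | 0.667 | 0.046 |
| 0.5 | 0.4/0.168 = 2.39 | 0.625 | 0.631 | 0.039 |
| 1.0 | 0.4/0.194 = 2.07 | 0.502 | 0.502 | 0.017 |

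With period, simulated power is 0.675 to 0.677 and type I error 0.049 to 0.051 at every d.

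**Range.** Over 16, 24 and 40 men and rho of 0.5, 0.7 and 0.9 (60,000 trials per setting), the largest power loss is 1.1, 4.9 and 17.4 percentage points at d = 0.25, 0.5 and 1.0. The smallest is about 0.

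**Cost of the term when there is no shift.** With balanced order it widens the 95% confidence interval by about 0.3% at 24 men and 1.5% at 12. It pays for itself once d exceeds about 0.10 at 24 men (0.23 at 12, 0.06 at 36).

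**Unequal orders.** Without period, the bias is (difference in order counts ÷ N) × d × sw. At an assumed 14:10 this is (4/24) × d × √0.3 = 0.023, 0.046 and 0.091 outcome SD for d = 0.25, 0.5 and 1.0, all below half of 0.2. With period the bias is zero. The adjustment then has a price: the standard error grows by 1/√(1 − (4/24)²) = 1.014. At an extreme assumed 9:3 in each group of 12, the unadjusted bias is 0.25 sw at d = 0.5 and 0.50 sw at d = 1.0, with type I error of 11% and 25%. The adjusted standard error is then 1/√(1 − 0.5²) = 1.155 times larger.

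**The case against.** The strongest reply is that nothing in the SAP is false here. The two-visit design is inferred, and order allocation would normally be in a protocol that is not shown. With balanced order the analysis is unbiased and errs on the cautious side, so leaving out a precision term is a defensible choice. The document gives no reason to expect a visit shift in any outcome. At 0.25 within-person SD the cost is negligible; the large losses need a shift of a full within-person SD, and 17 points is the worst cell of an assumed grid. The wear-time comparison proves little, since wear time adjusts for how long activity was recorded.

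Most of this stands as a limit on severity. The shift is unknown, the 1.0 SD case is an extreme, and bias is small unless the orders are badly unequal. Wear time shows only that the plan names extra terms where it wants them; it does not show that period was overlooked. The reply does not remove the point, however. Model terms are for the SAP to fix, and this one writes them out. On the natural reading of the design, omission gains almost nothing if there is no shift and loses precision if there is one.

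**Conclusion.** The point holds as an inexpensive improvement that should be made; it is not a fatal flaw. It rests on each man being measured under both conditions and would fall away in a parallel-group trial. With balanced order, the harm is a standard error larger by about 2%, 6% or 22% (closed form) at shifts of 0.25, 0.5 or 1.0 within-person SD. In the 24-man illustration that is a power loss of about 1, 4 or 17 percentage points, with no inflation of false positives. Bias arises only if the orders among the men analysed are unequal, and at 14:10 it stays under 0.1 outcome SD. Sample size, correlation, effect, order split and shift are all assumptions.

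**What to change.** Add one sentence to the third paragraph of the SAP: period (first or second main trial) enters as a fixed factor in every HOMA-IR, fasting, AUC and time-course model that contains condition. It should be settled before analysis, so that the choice does not depend on the results.

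The change needs only each man's visit order, which the trial should already hold. It uses about one degree of freedom: under half a percentage point of power in the balanced illustrations with no shift, and slightly more if the orders end up unequal, in return for removing the bias.

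### The smoker versus non-smoker contrast is not randomised, yet its models and its effect size adjust for no participant characteristic; age should be a pre-specified covariate

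*SAP*

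**What the plan says.** All the relevant text stands under the SAP's single heading, Statistical analyses plan.

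- **Risk-marker models (third paragraph).** HOMA-IR and the fasting and AUC plasma and blood pressure outcomes are analysed by linear mixed models "with condition (exercise versus control) and group (smokers versus non-smokers) included as fixed factors".
- **Time-course models (same paragraph).** Postprandial differences "will be examined using linear mixed models repeated for condition, group and time". No covariate is named.
- **The only covariate in the plan (same paragraph).** "Models for habitual physical activity and sedentary time will include wear time as a covariate". It serves those models alone.
- **Participant characteristics (second paragraph).** "Physical characteristics and exercise responses will be compared between smokers and non-smokers using linear mixed models with smoking status included as a fixed factor". They are treated as outcomes. The SAP does not list them and does not say what follows if they differ.
- **Effect size (last paragraph).** It is obtained by "dividing the difference between the mean values (exercise versus control or smokers versus non-smokers) with the pooled standard deviation", and without a clinical anchor "an effect size of 0.2 will be considered the minimum important difference". Significance is judged at P < 0.05.

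**The concern.** The two contrasts in this plan have different protection. Exercise versus control appears to be a comparison within each man, so stable characteristics such as age cancel. Smokers versus non-smokers is a comparison between men who were not allocated to their group, so nothing in the analysis removes a difference in who they are.

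Comparing characteristics between the groups does not fill that gap. In small groups a non-significant difference is compatible with an imbalance that matters, and a significant one triggers no action under this plan. A covariate that differs between the groups and is related to the outcome therefore goes straight into the group term, its P value and the effect size set against 0.2. A group difference that is partly or wholly one of age could then be reported as a smoking difference of important size.

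The absence of the protocol does not excuse this. The SAP itself lists the terms in each model, and names a covariate where it wants one, so the unadjusted group model is a stated choice.

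**Working it through.** The SAP states no sample size, power or imbalance, so it has no figure to reproduce. The check is a reading of the models followed by an illustration.

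**Inputs from the SAP:** model terms condition, group and, for time courses, time; group effect size from unadjusted means; minimum important difference 0.2; significance at P < 0.05, taken as two-sided.

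**Assumptions, not from the SAP:** one covariate; covariate difference d = 0.3 to 0.8 SD; within-group correlation with the outcome r = 0.3 to 0.5; n = 12 to 20 men per group; one outcome value per man; no true group effect.

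**Step 1: bias.** The spurious standardised group difference is r × d.

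- 0.3 × 0.3 = 0.09
- 0.4 × 0.5 = 0.20
- 0.5 × 0.5 = 0.25
- 0.5 × 0.8 = 0.40

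**Step 2: chance of P < 0.05 under a systematic difference.** With b = r × d and se = √(2/n), the rejection probability is Φ(b/se − 1.96) + Φ(−b/se − 1.96). Here se = √(2/12) = 0.408 and √(2/20) = 0.316.

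| d | r | b | n = 12: b/se | Rejection | n = 20: b/se | Rejection |
|---|---|---|---|---|---|---|
| 0.3 | 0.3 | 0.09 | 0.22 | 5.6% | 0.28 | 5.9% |
| 0.5 | 0.4 | 0.20 | 0.49 | 7.8% | 0.63 | 9.7% |
| 0.5 | 0.5 | 0.25 | 0.61 | 9.4% | 0.79 | 12.4% |
| 0.8 | 0.5 | 0.40 | 0.98 | 16.5% | 1.26 | 24.4% |

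The nominal rate is 5%. A correctly specified linear adjustment removes the r × d term.

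**Step 3: chance imbalance is a different matter.** With equal populations, an imbalance of at least 0.5 SD has probability 2 × [1 − Φ(0.5/se)]. This is 22% at n = 12 (0.5/0.408 = 1.22) and 11% at n = 20 (0.5/0.316 = 1.58). Such an imbalance biases that one study's estimate, given its sample, and adds variance. The test already allows for it: in simulation with equal populations the unadjusted test rejected 4.9% to 5.1% of the time.

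**Step 4: matching.** If the groups were matched exactly on the covariate, the group difference would have standard error se × √(1 − r²), while the unadjusted test still uses se. The rejection probability is then 2 × [1 − Φ(1.96/√(1 − r²))]. For r = 0.4 this is 3.2% (1.96/0.917 = 2.14) and for r = 0.5 it is 2.4% (1.96/0.866 = 2.26). Simulation gave 2.4% to 3.4%. The unadjusted test is then conservative: the omission costs precision and does not create false group differences.

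**The case against.** The strongest case against is that the harm depends on a protocol that is not at hand. Eligibility limits or matching on age or body size would normally be set there, and with good matching the unadjusted test is conservative. This stands as a limit on the size of the problem. It does not remove it: the SAP does not rely on matching, and if the groups are matched, the matching variables belong in the model to recover the precision.

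Four further points have weight.

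- **A reader might infer that chance imbalance in small groups inflates the false-positive rate.** It does not; only a systematic difference does, and nothing in the SAP shows one.
- **The 0.2 threshold is weak even without confounding.** With no effect at all, sampling error alone puts the group effect size beyond 0.2 in 62% of studies at n = 12 (0.2/0.408 = 0.49) and 53% at n = 20 (0.2/0.316 = 0.63). Adjusting for a covariate with r = 0.5 multiplies the standard error by 0.866 and leaves 57% and 47%. Adjustment removes the systematic shift; it does not make that threshold reliable.
- **The SAP speaks of differences, not of effects of smoking.** An unadjusted descriptive contrast is legitimate if it is labelled as one. The SAP neither labels it so nor offers an adjusted one.
- **Smoking may itself affect adiposity.** An adiposity-adjusted contrast could remove part of what is being studied. This is accepted, and it is why body size goes into a sensitivity model only.

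**Conclusion.** The concern holds as a risk of bias that the plan leaves open, and correcting it is a cheap improvement. The stated models and the group effect size take no account of any participant characteristic, so a systematic age or body-size difference that the design has not removed would enter the group contrast as r × d. Over the assumed ranges that is 0.09 to 0.40 SD. With 12 to 20 men per group, the chance of P < 0.05 with no smoking effect would be about 6% at the mild end (d = 0.3, r = 0.3) and 16% to 24% at the severe end (d = 0.8, r = 0.5).

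All of these figures rest on assumed d, r and n. A reader might go further and conclude that the groups do differ, or that the group results will be wrong. The SAP does not support that: it gives no imbalance and no sample size, and it does not describe how the men were recruited. Nor does the point reach the exercise versus control contrast, provided each man completes both conditions, which the wording suggests but does not state.

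**What to change.** 1. In the HOMA-IR, fasting, AUC, blood pressure and time-course models, pre-specify age as a covariate for the group contrast, together with any variable on which the protocol matches. Fix the choice before the data are seen, not from P values in the comparison of characteristics.
2. Add one body-size or adiposity measure in a sensitivity model, if it is among the physical characteristics recorded.
3. Compute the smoker versus non-smoker effect size from the adjusted difference. Otherwise the judgement against 0.2 stays unadjusted even when the models are corrected.
4. Report adjusted beside unadjusted group results, and describe the group result as an association with smoking status.
5. Leave the exercise versus control contrast as it is.

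The cost is a few sentences in the SAP and one or two between-man degrees of freedom. No new data are needed if age and the body-size measure are recorded, which is likely but not stated. The reported group difference may become smaller.
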